## 6 STUDY DESIGN

### 6.1 DESCRIPTION OF THE PROTOCOL

This trial is to be conducted as a multi-country, multi-center prospective, single arm, open-label, phase IIIb clinical trial.

After enrollment, patients will receive study treatment alirocumab 150 mg SC once every 2 weeks (Q2W) or 75 mg SC Q2W. The dose may be adjusted according to the investigator, based on treatment response.

Alirocumab will be administered on top of stable maximally tolerated statin therapy ±other LMTs over a period of at least 12 weeks and until the product becomes commercially available and reimbursed .

The investigator will manage, based on his/her own judgment and LDL-C value, adjustment of alirocumab doses (either up-titration from 75 to 150 mg every 2 weeks or down-titration from 150 to 75 mg every 2 weeks, or maintenance of the dose, will be possible). In case a modification of the current dose is decided, the patient will be contacted by the site staff and an unscheduled visit will be planned to dispense the new treatment kit and retrieve the current one.

The study consists of:

- A screening period of up to 3 weeks, including an injection training during which the patient or another designated person (such as spouse, relative, etc) will be trained to self-inject/inject). An optional dedicated visit could be scheduled as needed.
- An open-label treatment period with alirocumab of at least 12 weeks and until the product becomes commercially available and reimbursed. However, the open label treatment period will not exceed 30 months.
- An End-of-Treatment/End-of-Study visit will take place at least 2 weeks after last study treatment injection.

Patients should be on a stable diet (NCEP-ATPIII TLC diet or equivalent, see [Appendix A](#)) throughout the entire study duration from screening to the end of the study treatment.

Statin dose and dose regimen as well as dose and dose regimen of other LMTs (if applicable) should be stable throughout the whole study duration including the screening period.

Nevertheless, modification of LMT is allowed under certain conditions after enrollment as described in [Section 8](#).

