## 8 STUDY TREATMENTS

### 8.1 INVESTIGATIONAL MEDICINAL PRODUCT(S)

Sterile alirocumab drug product will be supplied at a concentration of 75 mg/mL and 150 mg/mL in histidine, pH 6.0, polysorbate 20, both as 1 mL volume in an auto-injector (also known as pre-filled pen).

Patient (or another designated person) will have to perform during the screening period (V1 or dedicated V2) or at the latest on V3 (Day 1) a placebo self-injection training, using a pre-filled pen, before the first alirocumab administration.

Injection for training: sterile placebo for alirocumab will be prepared in the same formulation as alirocumab without the addition of protein as 1 mL volume in a pre-filled pen, for the patients to perform an injection training.

Each alirocumab administration will consist of 1mL subcutaneous injection over the abdomen, thigh, or outer area of upper arm (ie, deltoid region).

The recommended dose is 75 mg or 150 mg administered subcutaneously once every 2 weeks (Q2W).

The dose selection should be based on individual patient characteristics and goal of therapy.

The dose can be adjusted based on treatment response. Lipid levels will be analyzed from Week 4, when maximum LDL-C reduction is usually achieved.

The Investigator is free to adjust the dose (up and down-titration) throughout the study based on clinical judgment.

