#### 9.2.1.1 Efficacy assessment method

##### 9.2.1.1.1 Lipid parameters

Total-C, HDL-C, TG, non-HDL-C will be directly measured by a local Laboratory as per the schedule in [Section 10.1](#).

LDL-C will be calculated using the Friedewald formula at all site visits.

Efficacy endpoints will not be considered as AEs, such as those involving abnormalities in lipid levels, unless meeting the criteria in [Section 10.4.2](#).

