### **Urine samplings:**

Urinalysis - dipstick will be performed at site or at the local Laboratory at screening, inclusion, W12, EOT/EOS visits and as needed during the study at investigator's discretion.

It will assess for pH, specific gravity, and for the presence of blood, protein, glucose, ketones, nitrates, leukocyte esterase, uro-bilinogen and bilirubin. If the dipstick is abnormal then standard microscopy will be conducted.

Notes: Any clinically relevant abnormal laboratory value should be immediately rechecked for confirmation before making any decision for the concerned patient. It should be documented as an AE/SAE if one or more criteria in [Section 10.4.2](#) are met. Please also refer to [Section 10.4.1.3](#).

Decision trees for the management of certain laboratory abnormalities by Sanofi are provided in [Appendix E](#), [Appendix F](#) and should be followed by investigators. In case of ALT increase  $\geq 3 \times$  ULN (or  $\geq 2 \times$  baseline ALT if ALT elevated at baseline), the local Laboratory will perform the required additional testing.

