#### **10.4.2 General guidelines for reporting adverse events (and product complaints)**

- All AEs, regardless of seriousness or relationship to investigational medical product (IMP)/ non investigational medical product (NIMP), spanning from the signature of the informed consent form until the end of the study as defined by the protocol for that patient, are to be recorded on the corresponding page(s) or screen(s) of the CRF.
- All products complaints associated or not to an AE are to be recorded immediately on the corresponding products (study medical device) complaints pages and reported to local Complaint Service immediately (within 24 hours).

- Whenever possible, diagnosis or single syndrome should be reported instead of symptoms. The Investigator should specify the date of onset, intensity, action taken with respect to IMP, corrective treatment/therapy given, additional investigations performed, outcome, and his/her opinion as to whether there is a reasonable possibility that the AE was caused by the IMP or by the study procedure(s).
- The Investigator should take appropriate measures to follow all AEs until clinical recovery is complete and laboratory results have returned to normal, or until progression has been stabilized, or until death, in order to ensure the safety of the patients. This may imply that observations will continue beyond the last planned visit per protocol, and that additional investigations may be requested by the monitoring team up to as noticed by the Sponsor.
- Patients who experience an ongoing SAE or an AESI, at the prespecified study end-date, should be followed until resolution, stabilization, or death and related data will be collected. The duration of post study follow-up and reporting of AEs will be specified (eg, until recovery).
- When treatment is prematurely discontinued, the patient will have an EOT (=EOS) visit at least 2 weeks after the last study treatment injection unless there is an AE to be followed until final outcome and related data will be collected.
- Laboratory or vital signs are to be recorded as AEs only if:
  - Symptomatic and/or,
  - Requiring either corrective treatment or consultation, and/or,
  - Leading to IMP discontinuation or modification of dosing, and/or,
  - Fulfilling a seriousness criterion, and/or,
  - Defined as an AESI.

Instructions for AE reporting are summarized in [Appendix E](#).

- Adverse event (injection site reactions) recorded in patient's questionnaire:  

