## Appendix E    Summary of Adverse Events reporting instructions at Sanofi

[figure not shown]
EVENT CATEGORY	REPORTING TIMEFRAME	SPECIFIC EVENTS IN THIS CATEGORY	CASE REPORT FORM COMPLETION		
			AE form	Safety complementary Form a	Other specific forms
Adverse event (non-SAE, non-AESI)	Routine	Any AE that is not SAE or AESI	Yes	No	No
Serious Adverse Event (non-AESI or AESI)	Expedited (within 24 hours)	Any AE meeting seriousness criterion per Section 10.4.1.2	Yes	Yes	No, unless applicable
Adverse Event of Special Interest (AESI)	Expedited (within 24 hours)	Pregnancy of female patient/subject (including male subject's partner as described in Section 10.4.1.3 )	Yes	Yes	Yes
		Symptomatic overdose with IMP	Yes	Yes	No
		Increase in ALT as follows: - ALT $\geq 3$ ULN (if baseline ALT <ULN) or - ALT $\geq 2$ times the baseline value (if baseline ALT $\geq$ ULN) Please refer to related flowchart (per Appendix C )	Yes	Yes	Yes
		Allergic drug reactions and/or local injection site reactions deemed to be allergic and requiring consultation with another physician as specified in Section 10.4.1.3 .	Yes	Yes	Yes b
		Neurologic events (requiring additional examinations/procedures and/or consultation with a specialist as specified in Section 10.4.1.3 )	Yes	Yes	Yes
		Neurocognitive events ( Section 10.4.1.3 )	Yes	Yes	Yes
		Non-allergic or allergic not requiring consultation with another physician, as described in Section 10.4.1.4 .	Yes	No	Yes b
Local injection site reaction	Routine				

EVENT CATEGORY	REPORTING TIMEFRAME	SPECIFIC EVENTS IN THIS CATEGORY	CASE REPORT FORM COMPLETION		
			AE form	Safety complementary Form a	Other specific forms
Laboratory or vital sign abnormality (non-SAE, non-AESI) that is: - Symptomatic - Requiring corrective treatment or consultation - Leading to IMP discontinuation or dose regimen modification	Routine	- Neutropenia - Thrombocytopenia - Acute renal insufficiency - Increase in CPK and suspicion of rhabdomyolysis Per Appendix C .	Yes	No	No

- a. Completion of a Safety Complementary Form is required for any AE meeting a seriousness or AESI criterion, even if this is not otherwise required according to the table for a particular type of AE

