##### ***2.4.4.2 Analyses of secondary efficacy endpoints***

Efficacy variables will be analyzed in the mITT population through descriptive statistics. No formal statistical comparisons will be performed for efficacy variables.

Quantitative descriptive summaries (number of available data, mean, SD, median, Min and Max) by planned time points will be presented for all lipids using observed (ie, non-missing) data. Missing data will not be imputed. In addition, standard error (SE) and the 95% CI for the mean will be provided for lipids other than TGs and Q1 and Q3 will be provided for TGs. The computation of the 95% CI will be based on a normal distribution or a Student distribution depending on the number of patients.

For all continuous secondary efficacy endpoints (LDL-C, non-HDL-C, total-C, HDL-C and triglycerides), percent changes from baseline using number of available data, mean, SD, median, Min, and Max will be displayed. For percent changes, 95% CI of the mean will also be provided.

The proportions of patients reaching the different targets defined for LDL-C (see [Section 2.1.3.2](#)) will be provided with their corresponding 95% CI. In case of a number of patients deemed insufficient, the Clopper-Pearson algorithm will be used to compute the 95% CI.

All measurements, scheduled or unscheduled will be assigned to analysis windows defined in [Section 2.5.4](#).

Regarding the patterns of up-titration/down-titration, the proportions with their corresponding 95% CI, will be provided for the following categories:

- Patients with at least one up-titration to 150 mg of alirocumab during the observational period. The time from the initiation of alirocumab at 75 mg to the first up-titration to 150 mg will be quantitatively described and the reasons that triggered the change of dosage will be displayed (AE, Lipid values or others).
- Patients with at least one down-titration to 75 mg of alirocumab during the observational period. The time from the initiation of alirocumab at 150 mg to the first down-titration to 75 mg will be quantitatively described and the reasons that triggered the change of dosage will be displayed (AE, Lipid values or others).
- Patients with a dose of alirocumab unchanged at 75 mg during the observational period and the duration of treatment without changes of doses.
- Patients with a dose of alirocumab unchanged at 150 mg during the observational period and the duration of treatment without changes of doses.

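### The AE recording rule can turn a planned LDL-C-driven dose change into an adverse event, while the titration endpoint treats the two as separate, and the SAP has no rule for such records

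*Protocol*

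**What the plan says.** **Recording rule.** Protocol 10.4.2 introduces its list with "Laboratory or vital signs are to be recorded as AEs only if". The grounds are joined by and/or, so one is enough, and one of them is "Leading to IMP discontinuation or modification of dosing". The notes in Protocol Section 10 (under urine samplings) say of a clinically relevant abnormal laboratory value: "It should be documented as an AE/SAE if one or more criteria in" Section 10.4.2 are met. Appendix E has a matching row, "Leading to IMP discontinuation or dose regimen modification", with the AE form marked Yes.

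**Lipid exemption.** Protocol 9.2.1.1.1: "Efficacy endpoints will not be considered as AEs, such as those involving abnormalities in lipid levels, unless meeting the criteria in" Section 10.4.2.

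**Planned titration.** Protocol 6.1: "The investigator will manage, based on his/her own judgment and LDL-C value, adjustment of alirocumab doses", in either direction. Protocol 8.1: "The Investigator is free to adjust the dose (up and down-titration) throughout the study based on clinical judgment".

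**Titration reasons.** Protocol 9.2.2 names LDL-C threshold and AE as distinct reasons. SAP 2.4.4.2 does the same: "the reasons that triggered the change of dosage will be displayed (AE, Lipid values or others").

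**Analysis.** AEs are part of the primary endpoint (Protocol 9.1). SAP 2.1.4.1 reports every AE the investigator diagnoses, and SAP 2.4.5.1 tabulates all TEAEs. Neither says what to do with an AE record that consists of an LDL-C value and a dose change.

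**The concern.** The exemption that keeps lipid values off the AE form refers back to a list that includes dose modification. In this trial the dose is meant to follow the LDL-C value. A single LDL-C result that prompts titration can therefore be both an AE under 10.4.2 and the non-AE reason under 9.2.2.

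Two outputs are exposed:

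- **TEAE tables.** The expected drug effect, or a shortfall from it, could be counted as a TEAE. SAP 2.5.3 also counts an AE with missing causality as related. The study has one open-label arm, so no control group would reveal inflation from a recording rule. Sites that read the text differently would report different AE rates.
- **Titration reasons.** The split between AE and lipid values would partly reflect how each site read the rule.

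**Working it through.** **1. The passages side by side.** Take an LDL-C value that the investigator judges abnormal and clinically relevant and that leads only to an alirocumab dose change.

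- Under 9.2.1.1.1 it is exempt unless it meets a 10.4.2 ground.
- Under 10.4.2 it meets one, modification of dosing, so the exemption lapses.
- Under the Section 10 notes, meeting one ground means it should be documented as an AE.
- Under 9.2.2 and SAP 2.4.4.2 the same event belongs to the lipid category, as distinct from AE.

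The last line does not fit with the first three.

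**2. Down- and up-titration differ.** Protocol 11.4.2 and SAP 2.1.4.1 count an AE as treatment-emergent only if it began, got worse or turned serious in the TEAE period. A very low LDL-C on treatment is new. A high LDL-C that has fallen from baseline but missed the goal is not: entry already required at least 100, 130 or 160 mg/dL (Protocol 7.1). It enters the TEAE tables only if a site records it as a new event with an on-treatment onset.

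**3. The plan's own precision.** Half-width = 1.96 × √(p(1−p)/1300).

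- p = 10%: 1.6 points, giving 8.4 to 11.6%.
- p = 50%: 2.7 points, giving 47.3 to 52.7%.

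All five intervals in the protocol's Table 1 reproduce. At p = 61.1% the half-width is 2.65 points, and at p = 78.6% it is 2.23.

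**4. Size, as an illustration.** Inputs:

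- N = 1300 (Protocol 11.1).
- Background TEAE rate b = 61.1% (ODYSSEY HIGH FH) to 78.6% (ODYSSEY LONG TERM), both from Protocol Section 4. Both are 150 mg Q2W studies.
- Assumed: half of patients start on each dose.
- Assumed: 5 to 15% of 150 mg starters are down-titrated on LDL-C.
- Assumed: 20 to 50% of 75 mg starters are up-titrated on LDL-C. The only related figure in the documents is 54/109 = 49.5%, from ODYSSEY ALTERNATIVE, where titration was automatic.
- Assumed: every such change is recorded as an AE, independently of other TEAEs.

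Share with a titration-only AE:

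- Down-titration only: t = 0.5 × 5% = 2.5% to 0.5 × 15% = 7.5%.
- Both directions: t = 0.5 × 20% + 2.5% = 12.5% to 0.5 × 50% + 7.5% = 32.5%.

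Rise in any TEAE = t × (1 − b), in percentage points:

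| Recorded as AE | t | Patients | b = 78.6% | b = 61.1% |
|---|---|---|---|---|
| Down only | 2.5% | 33 | 0.5 | 1.0 |
| Down only | 7.5% | 98 | 1.6 | 2.9 |
| Down and up | 12.5% | 163 | 2.7 | 4.9 |
| Down and up | 32.5% | 423 | 7.0 | 12.6 |

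Independence matters. If every titrated patient already had another TEAE, the rise in any TEAE is zero. With no overlap it is t itself, capped at 100% − b.

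**The case against.** The case on the other side is substantial.

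- **The list sets a necessary condition.** Section 10.4.2 says when a laboratory value may be an AE, not that it must be. The duty to record comes from the Section 10 notes, which apply only after the value is judged clinically relevant and abnormal. Protocol 10.4.1.1 also requires an untoward occurrence, and a planned response adjustment is not obviously one. This stands. A reader might infer that every LDL-C value leading to a dose change is an AE, but the documents do not go that far.
- **Appendix E lists no lipid event.** Its dose-modification row names neutropenia, thrombocytopenia, acute renal insufficiency and CPK increase. This stands and weakens Appendix E as support, but 10.4.2 and the Section 10 notes carry no such limit.
- **The exemption still does useful work.** It keeps off the AE form the many abnormal lipid values that lead to no action. This stands.
- **Up-titration after an improved LDL-C is arguably not treatment-emergent.** This stands as a reading of the definition, and it is why down-titration is shown separately above.
- **Intent is clear and the records can be found.** Titration reasons are listed apart from AEs, TEAEs are tabulated by preferred term, and SAP 2.4.4.4 analyses very low LDL-C and later dose changes. This limits the damage. It does not correct the any-TEAE line or tell sites what to record.
- **Capturing very low LDL-C as an AE may be deliberate.** Protocol Section 4 says the safety of such values is still under assessment. If so, the text should say so, and the titration reasons should be aligned with it.

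**Conclusion.** The passages conflict and need to be reconciled. As written they allow, and read literally direct, a site to record as an AE an LDL-C value judged clinically relevant and abnormal whose only consequence is a planned titration. The titration endpoint assumes the two are separate, and the SAP does not say how to handle the overlap.

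The actual effect on AE rates cannot be known from the documents. On the assumptions above, down-titration alone adds about 0.5 to 2.9 points to any TEAE, so it passes the planned half-width of about 2.2 to 2.7 points only at the top of its range. If up-titration is recorded as well, the rise is about 2.7 to 12.6 points, at or above the half-width throughout. These figures assume full literal recording. Partial adherence gives smaller rises, spread unevenly across sites.

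A reader might also infer that this trial's AE rates cannot be compared with those of earlier alirocumab trials. The documents do not give those trials' recording rules, so comparability is uncertain rather than ruled out.

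**What to change.** **Protocol and eCRF guidance.** In 9.2.1.1.1, the Section 10 notes, 10.4.2 and Appendix E, state whether an LDL-C value whose sole consequence is a planned alirocumab titration is recorded as an AE or only as the titration reason. Make 9.2.2 agree. Leave the other 10.4.2 grounds as they are: symptoms, corrective treatment or consultation, seriousness, AESI status and discontinuation.

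**SAP.** In 2.4.4.2, assign each LDL-C-driven dose change to one reason, lipid values. In 2.4.5.1, present the TEAE summaries with and without LDL-C terms whose only action was titration. This also covers records already collected, since enrollment began on 08 July 2015 (SAP 1.5), and it keeps very low LDL-C cases visible.

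**Cost.** One extra summary and a small change to the eCRF guidance. No new data are needed and no safety information is lost.

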#### **10.4.3 Instructions for reporting serious adverse events**

In the case of occurrence of an SAE, the Investigator or designee must immediately:

- ENTER (within 24 hours) the information related to the SAE in the appropriate screens of the e-CRF; the system will automatically send a notification to the monitoring team after approval of the Investigator within the e-CRF or after a standard delay.
- SEND (preferably by fax or e-mail) a photocopy of all examinations carried out and the dates on which these examinations were performed, to the representative of the monitoring team whose name, fax number, and email address appear on the clinical trial protocol. Care should be taken to ensure that the patient's identity is protected and the patient's identifiers in the clinical trial are properly mentioned on any copy of a source document provided to the Sponsor. For laboratory results, include the laboratory normal ranges.

- All further data updates should be recorded in the e-CRF as appropriate, and further documentation as well as additional information (for laboratory data, concomitant medications, patient status, etc.) should be sent (by fax or e-mail) to the monitoring team within 24 hours of knowledge of the SAE. In addition, every effort should be made to further document any SAE that is fatal or life threatening within a week (7 days) of the initial notification.
- A back-up plan (using a paper CRF process) is available and should be used when the e-CRF system does not work.

Any SAE brought to the attention of the Investigator at any time after the end of the study for the patient and considered by him/her to be caused by the IMP with a reasonable possibility, should be reported to the monitoring team.

#### **10.4.4 Guidelines for reporting adverse events of special interest**

For these AEs, the Sponsor must be informed immediately (ie, within 24 hours), as per SAEs notification described in [Section 10.4.3](#), even if not fulfilling a seriousness criterion, using the corresponding screens in the e-CRF. Please refer to [Section 10.4.1.3](#) for a listing of AESI and [Appendix E](#) for a summary of reporting adverse events.

For each defined AESI, the Investigator or any designees must make every attempt to collect additional specific information such as:

- Preexisting related condition or lifestyle of interest for the AE (eg, habits, CV risk factor).
- Expected list of associated signs and symptoms.
- Corrective actions (eg, treatment discontinuation, concomitant treatment).
- Diagnostic actions (eg, test[s] or procedure[s] results).
- Additional descriptive factors.
- Sequelae.

#### **10.4.5 Guidelines for management of specific laboratory abnormalities**

Decision trees for the management of certain laboratory abnormalities by Sanofi are provided in [Appendix F](#).

The following laboratory abnormalities should be monitored, documented, and managed according to the related flow chart in protocol appendices.

- Neutropenia.
- Thrombocytopenia.
- Increase in ALT.
- Acute renal insufficiency.
- Increase in CPK and suspicion of rhabdomyolysis.

